The primary hypothesis is that PASC reduce complications up to 30 days after surgery. Secondary hypotheses are that PASC reduce readmissions to hospital, length of hospital stay, and mortality up to 30 days after surgery.

Complications are in this trial observations of the surgical complications registered in patients' medical records and coded according to the International Classification of Diseases – 10th version (ICD-10) by surgeons or ward doctors. One or more complications per hospital stay per patient will be given the values zero or one, as the main outcome variable. Similarly, secondary outcomes. i.e. mortality, will be given zero or one (for events).

Statistical power

In protocol version 1.0, the sample size was calculated to be 4200 cases across the clusters. Based on data from a pilot of PASC feasibility (Harris et al, 2023), an update was required. The sample size analysis was updated in protocol 2.0 (30th June 2021):

The pooled overall proportion of surgery-related complications (i.e. infections, bleedings, cardiac or lung related) has previously been estimated to be 15% and is the primary outcome for the present analysis (Storesund et al, 2020). We propose that the inclusion of PASC will lower this proportion by at least 5% (corresponding to a 33.3% relative risk reduction). Using the stepped wedge power analyses command in Stata (*steppedwedge* command), we calculated that the lowest number of individuals required to detect the 5% reduction is 5320. The calculation was carried out using a non-standard stepped wedge design (see diagram below): 7 wards x 20 months x 38 patients (on average). We further assumed that the intra-cluster correlation (ICC) was 0.05 and that the type I error and type II error were 0.05 and 0.20, respectively.

Statistical analyses

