Descriptive statistics: Descriptive statistics, including percentage and means with 95% confidence intervals, will be used to quantify sample characteristics of the participating wards and participants. To investigate potential bias in characteristics due to self-selection, characteristics for participants and the source population will be compared for each participating wards. We will further quantify bias by calculating the ratio of proportions for categorical data and difference in means for continuous data. *Analytical statistics:* For investigating the effects of PASC on surgery-related complications, we will use binary logistic regression models using the control period as reference category. Correlation between outcomes on the same hospital (ICC) will be considered by including a random intercept for the hospitals

in the various models (exchangeable correlation assumed). To account for potential temporal trends in the outcome, we will include calendar month as a continuous (linear or nonlinear) term in all models. Additional adjustment would be required if selection bias is present.

Variables are gender (0/1), age (in years), comorbidity (ASA-classification 1-5), type of anesthesia (general, spinal/regional, or combination – nominal scores), type of surgery (nominal scores), length of surgery (knife-time in minutes/hours), type of hospital (nominal scores), and month of surgery (1-27). Outcome variables: complication (one or more) up to 30 days after surgery, readmission to hospital within 30 days, mortality up to 30 days after surgery, and length of hospital stay.

Non-response and selection bias

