Preliminary data collection suggests that the participation rate for PASC is 50% (Harris et al, 2022). If participation probability is associated with characteristics that also are related to the outcome under study, effects of PASC on surgery-related complications could be biased. In the table example below, the risk of complication in complete data with no self-selection would be 15% and 10% for the control and intervention periods, respectively. With 50% non-response (and strong selection on characteristics) in the intervention period, the corresponding risk of complication could be only 5%. Thus, a large risk reduction in the intervention period could be ascribed selection rather than the intervention. Fortunately, our study is prospective in that the outcome is measured after the intervention take place. Accordingly, only the difference in patient characteristics between control and intervention period can affect the difference in future outcome. Following this, regression adjustment for difference in patient characteristics would probably be sufficient to adjust for selection bias (1).

Protocol deviation and intention to treat (ITT)

Protocol violations for the PASC intervention may include incomplete response to questionnaire, not operated after all, or other aspects that might imply that the patients should not be included for analyses. In such cases, we will still include subjects as if they had been treated (intention to treat analyses). If we were to exclude patients due to protocol violation (per protocol analysis), this could lead to serious bias which is not possible to correct using adjusted regression analyses.

This description of statistical analysis and power analysis was performed by biostatistician and [name] [name] in collaboration with [name] [name], in the updated 2.0 version of the protocol.

Reference

- Harris et al. Development and validation of patients' surgical safety checklist. BMC Health Services Research. 2022; 22:259.
- Harris et al. Feasibility of implementing a surgical patient safety checklist: prospective cross-sectional evaluation. Pilot and Feasibility Studies (2023) 9:52
- Storesund A, et al. Clinical Efficacy of Combined Surgical Patient Safety System and the World Health Organization's Checklists in Surgery - A Nonrandomized Clinical Trial. JAMA Surgery. 2020;155(7):562-570.

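### The intention-to-treat rule keeps patients who were never operated, is worded only for PASC, and could favour PASC if the control period is not handled the same way

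*SAP*

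**What the plan says.** All references are to the SAP, plan a).

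- **Protocol deviation and intention to treat (ITT).** The section opens with a list of possible grounds for leaving a patient out: "Protocol violations for the PASC intervention may include incomplete response to questionnaire, not operated after all, or other aspects". The instruction that follows is "In such cases, we will still include subjects as if they had been treated (intention to treat analyses"). The reason given against exclusion is that "this could lead to serious bias which is not possible to correct using adjusted regression analyses".
- **Hypothesis.** "The primary hypothesis is that PASC reduce complications up to 30 days after surgery". The coding is "One or more complications per hospital stay per patient will be given the values zero or one, as the main outcome variable", taken from ICD-10 codes for surgical complications in the medical record.
- **Statistical analyses.** For the effect on complications, "we will use binary logistic regression models using the control period as reference category". A random intercept for hospital and a calendar-month term are promised for the models. The variable list includes type of anaesthesia, type of surgery, knife-time and month of surgery. The outcome list gives "complication (one or more) up to 30 days after surgery" and also times mortality after surgery; readmission is within 30 days, with no stated link to an operation.

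Plan a) does not say how the outcome or day 0 is set for a retained patient who had no operation. It does not say whether control-period patients whose operation was cancelled are identified and kept.

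**The concern.** A patient who was not operated is hardly at risk of the primary outcome. Putting such patients into one side of the comparison lowers that side's complication rate whatever the checklist does. The rule is framed around violations of the PASC intervention, so a literal reader applies it to intervention-period patients and finds nothing to apply to the controls. The same section of the SAP is rightly wary of false risk reductions caused by selection in the intervention period. This rule could let one in by another route.

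The rule also sits badly with the listed covariates. A non-operated patient has no month of surgery and no knife-time, and the anaesthesia categories have no level for none. Plan a) states no missing-data rule, so a complete-case model using any of these variables drops the very patients that the ITT rule keeps. The analyst would then have to choose a month, a day 0 and an outcome code after the fact.

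**Working it through.** **Plan's own figures.** 7 wards × 20 months × 38 patients = 5320, as stated. 5/15 = 33.3% relative reduction, as stated.

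**Inputs from the SAP.** Control risk 15%, target risk 10%, ICC 0.05, 38 patients per ward-month (plan a, Statistical power).

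**Assumed.** q, the share of a group not operated. The SAP gives no figure, so 2%, 5% and 10% are shown. Non-operated patients are taken to score 0. The test is taken as two-sided at 0.05, because plan a) does not state sidedness.

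**Formulas.** Observed risk = p × (1 − q). With shares q_P (PASC) and q_C (control) and no true effect, the false risk difference is p × (q_P − q_C). Odds ratio = [a/(1 − a)] / [b/(1 − b)], where a is the observed PASC risk and b the observed control risk.

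**Case 1: kept in the PASC group only, no true effect (b = 0.15).**

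| q | observed PASC risk | false difference | share of 5-point target | odds ratio |
|---|---|---|---|---|
| 2% | 0.15 × 0.98 = 14.7% | 0.30 points | 6% | (0.147/0.853)/(0.15/0.85) = 0.977 |
| 5% | 0.15 × 0.95 = 14.25% | 0.75 points | 15% | (0.1425/0.8575)/(0.15/0.85) = 0.942 |
| 10% | 0.15 × 0.90 = 13.5% | 1.50 points | 30% | (0.135/0.865)/(0.15/0.85) = 0.884 |

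**Chance of a significant result favouring PASC in case 1** (2.5% if unbiased). The design diagram is not available, so one layout is assumed: seven wards crossing over after 2, 5, 7, 10, 12, 15 and 17 of 20 months. The Hussey–Hughes variance with ICC 0.05 and 38 per ward-month gives a standard error of about 1.65 points. The chance is Φ(difference/SE − 1.96):

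- q = 2%: Φ(0.18 − 1.96) = 3.8%
- q = 5%: Φ(0.45 − 1.96) = 6.6%
- q = 10%: Φ(0.92 − 1.96) = 14.9%

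Another layout would change these three figures but not the table.

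**Case 2: kept in the PASC group only, true 15% against 10%.** At q = 5%, 15 − 10 × 0.95 = 5.5 points. At q = 10%, 15 − 10 × 0.90 = 6.0 points. The benefit is exaggerated.

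**Case 3: kept equally in both periods.** With no true effect both risks are 0.15 × (1 − q), so the odds ratio is 1.00 at every q. With a true 15% against 10%, the difference at q = 5% is 14.25 − 9.5 = 4.75 points, and at q = 10% it is 13.5 − 9.0 = 4.5 points. The risk ratio stays at 0.667; the odds ratio moves only from 0.630 to 0.632 and 0.634.

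**Case 4: unequal but two-sided, no true effect.** With 5% in the PASC group and 2% in control, 15 × (0.05 − 0.02) = 0.45 points in favour of PASC. The sign follows whichever group holds more such patients: with 5% in control only, the odds ratio is 1.06, against PASC.

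**The case against.** A reader might infer that the rule as written does bias the primary result towards PASC. The SAP does not support that. Violations may be listed for PASC simply because control patients have no checklist to deviate from. Nothing says that cancelled control patients are left out, and how controls are identified may be set in the protocol. With equal retention there is no false effect. This objection stands, and the direction of bias must stay conditional.

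A reader might also infer that the ITT set and the model cannot be used together. That goes too far. Only the calendar-month term is promised for all models, and it could be taken from an admission or scheduled date. Further adjustment is conditional on selection bias being present. The conflict is real only for models that use month of surgery, knife-time or another operation-dependent variable. In a complete-case fit of such a model the non-operated patients drop out and cannot bias it, so the possible bias belongs to models that keep them.

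Nor are all outcomes fixed at zero. Readmission is not tied to an operation, and a stay without surgery could still carry an ICD-10 code for an infection or a cardiac event. For the primary outcome, zeros are near-certain but not guaranteed.

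Finally, retention has a legitimate purpose. PASC is used before surgery and may prompt visits to a general practitioner or dentist (plan d), so it might change who is operated. Leaving out non-operated patients then conditions on an event after exposure. This stands as a cost of the remedy. It does not justify a rule stated for one side only.

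**Conclusion.** The point holds in conditional form. The SAP expressly keeps non-operated patients in the primary comparison, although its primary outcome is timed from surgery. It states the rule only for PASC and leaves their outcome coding and day 0 undefined.

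If such patients are kept only, or more often, in the PASC group, the result tilts towards PASC: by 0.3, 0.75 or 1.5 points at an assumed 2%, 5% or 10% in PASC alone. If they are kept equally, the cost is only a diluted risk difference. The SAP does not settle which case applies, and the shares are assumptions. Separately, models using month of surgery or knife-time would drop these patients, contrary to the ITT rule. This should be put right before the primary analysis is run.

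**What to change.** Replace the one-sided rule with one population definition applied identically in control and intervention periods, with patients classified by their ward's randomised condition at the time. An example is all enrolled patients who had surgery. Patients with incomplete checklists or questionnaires stay in, as the SAP intends.

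Run the alternative population as a sensitivity analysis: all scheduled patients, provided they are captured in both periods, with month taken from the scheduled or admission date and the outcome coding for non-operated patients stated. Report the number not operated by period.

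The cost is a few sentences of SAP text and, for the sensitivity analysis, records of cancelled operations in both periods. The downside is that an operated-only set conditions on a post-exposure event and could itself be selective if PASC changes who is operated. The sensitivity analysis and the counts by period are there to show whether that happened.

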The main goals of the study are to investigate the impact of a patient safety checklist on patients having surgery within different surgical specialties, in three Norwegian hospitals (rural, central, and university hospital). The study has several work packages and hypothesis: a) The PASC checklist is hypothesized to have effect on surgical patients’ complications, reoperations, readmissions, length of stay and mortality. Of these variables, complications are the primary outcome. Further, patients’ experiences are hypothesized to be positively impacted by using PASC. Primary outcome for this part is the Patient Safety Checklist Experience Questionnaire. b) One part of the PASC checklist project include patients’ self-screening on their risk of malnutrition, prior to surgery. Main hypothesis is that the PASC have impact on nutritional outcomes. Nutritional complications are a primary outcome for this part of the study, and secondary outcome are comparison of patients and healthcare staffs’ risk assessments by comparing use of the Malnutrition Screening Tool. c) Investigate how implementation of the PASC checklist, a patient safety intervention, may be optimally used by the patients. Primary outcome is feasibility and compliance to using the checklist. Further, patients experiences are hypothesized to be positive towards the implementation. Primary outcome of this part is the PASC implementation survey. d) PASC is hypothesized to have an impact on cost-benefit of patients and the healthcare services. For this part of the study, the primary outcome is cost-effectiveness of the implementation across a-c. Secondary outcomes are the patient costs attributed associated with their surgical treatment. e) The PASC checklist is hypothesized to have impact on patients’ health literacy. Primary outcome is the nine dimensions of the Health Literacy Questionnaire. f) PASC is hypothesized to have impact on patients’ Quality of Life. Primary outcome is the EuroQual-5D-3L questionnaire.

Explanations of the statistical analysis techniques used for analyzing the data in the trial are detailed in the pages below.

Reference

Harris et al. Development and validation of patients’ surgical safety checklist. BMC Health Services Research. 2022; 22:259.

Statistical analysis plan a) for the PASC Stepped Wedge Cluster Randomized Controlled Trial

Hypothesis

[figure not shown]

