The main hypotheses for these parts of the study are that PASC have positive impact on patients experiences with using the checklist and the implementation of it. Hence, primary outcomes of these two studies are the PASC experience questionnaire (PASC-EQ) and the PASC implementation questionnaire (PASC-IQ).

The survey instruments

The PASC-EQ instrument was developed to measure patients' experiences with using the patient safety checklist in the intervention arm ([name] 2017). The development was based on literature searches (Harris et al. 2020, Harris et al. 2022) and expert review of items suggested

by the research group. Items were reviewed by clinicians and researchers within patient safety and surgical safety checklists research group of PASC.

The PASC-EQ consists of 21 items representing 5 domains of patients' experiences with using the patient safety checklist (PASC). The domains are labelled as 1: Information on my surgery. 2: Patient safety. 3: Patient involvement. 4: Communication with healthcare personnel. 5: Engaging with healthcare services.

For the PASC Implementation Questionnaire (PASC-IQ) we added three dimensions, each with four items, to the survey. These items were inspired by the implementation form used by Weiner and colleagues (2017) and adapted for investigating the PASC implementation experiences.

For both questionnaires, all scores went from 'Disagree totally', 'Disagree', 'Nor disagree or agree', 'Agree', and 'Agree totally' (values 0-4).

Statistical power of the PASC trial on the PASC-EQ and PASC-IQ

According to Kline (2011, p. 225) the sample size required to perform Structured Equational Modelling (SEM) usually requires 3-400 cases for models when degrees of freedom are <10. With higher degrees of freedom, i.e. > 20, a smaller number of cases is required for a minimum power of 0.80. However, the sample size should never be less than 100 in any event (Kline, 2011). The degrees of freedom within PASC-EQ/PASC-IQ data, including 7 surgical clusters, are estimated to be 32. Accordingly, more than 200 cases (respondents) are a sufficient sample for conducting SEM (confirmatory factor analysis) with PASC-EQ/PASC-IQ data.

Statistical analysis

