Descriptive statistics (i.e. frequencies, percentages, mean, standard deviations) will be used to assess patients' characteristics. To investigate the PASC-EQ/PASC-IQ impact on patients' experiences, chi-squared test will be used to test any differences between the intervention clusters, and patient characteristics. Independent samples t-test (ANOVA) will be used to investigate mean score difference between groups and patient characteristics as appropriate. If there are significant variation in patients' characteristics between the groups, linear regression model (General Linear Model) will be applied to adjust for it and to compare across the PASC-EQ/PASC-IQ domains. Missing data will be managed by creating 200 imputed datasets and the imputation model included all variables that to be included in adjusted regression model.

The validity and reliability of the questionnaires will be investigated. For the internal consistency of PASC-EQ/PASC-IQ Cronbach's alpha (scores between 0 and 1, preferably >0.7) will be applied. Spearman's rho will be used to assess correlations between the dimensions. Explanatory factor analysis and indicators will be assessed. Psychometric evaluation will be performed by measuring the hypothesized structure model with fit indicators as χ^2 , CFI, TLI, and RMSEA (Bollen 1989, Kline 2011). These analyses will be performed in IBM SPSS version 29 and IBM SPSS AMOS version 26, and a two-sided P value at 0.05 will be considered statistically significant.

The description of the planned statistical analyses, including the sample power analyses, were originally performed for the 2.0 protocol update, by [name] [name], Department of Anaesthesia and Intensive Care, Haukeland University Hospital, Bergen,

Norway; and Faculty of Health Sciences, Department of Nursing and Health Promotion, Acute and Critical Illness, Oslo Metropolitan University, Oslo, Norway.

The text was up-dated 30th August 2024 prior to analysis, by [name] [name].

References

Bollen K. Structural equations with latent variables. Wiley-Interscience publication. Mexico. 1989. ISBN 0-471-01171-1.

[name]. Development and Implementation of Patient Safety Checklists Before, During and After In-hospital-Surgery a Stepped Wedge Cluster Randomized Controlled Trial. ClinicalTrial.govID:NCT03105713). 2017.

Harris et al. Patients' and healthcare workers' recommendations for a surgical patient safety checklist – a qualitative study. BMC Health Services Research. 2020; 20:43.

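### The PASC-EQ and PASC-IQ hypotheses claim a positive impact of PASC, but the named tests compare wards, patient subgroups and undefined groups, and no comparator or reference score is given

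*SAP*

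**What the plan says.** The section of the SAP on the PASC-EQ and PASC-IQ opens with its main hypotheses, that "PASC have positive impact on patients experiences with using the checklist and the implementation of it". It names the two questionnaires as the primary outcomes of these parts of a) and c).

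Under *The survey instruments*, the PASC-EQ is described as built to capture patients' experiences with "using the patient safety checklist in the intervention arm". The PASC-IQ consists of three further dimensions of four items each, added to the survey and adapted to the PASC implementation. All items are scored 0 to 4, from total disagreement to total agreement.

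Under *Statistical analysis*, the impact on experiences is to be investigated as follows: a "chi-squared test will be used to test any differences between the intervention clusters, and patient characteristics". A t-test or ANOVA of mean scores between groups and patient characteristics follows. If characteristics vary between the groups, a linear model is used to adjust and to compare across domains. The word *groups* is not defined.

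The SAP's opening summary of work packages words the two hypotheses differently. Under a), "patients’ experiences are hypothesized to be positively impacted by using PASC". Under c), "patients experiences are hypothesized to be positive towards the implementation".

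**The concern.** A claim that PASC has a positive impact needs a contrast with patients not exposed to PASC. A claim that experience is positive needs a reference score. The section states neither, and the tests it assigns to the question address heterogeneity among respondents.

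This matters because these are primary outcomes of two sub-studies. If the plan is followed as written, a significant result means that wards or patient subgroups score differently. A non-significant result is equally compatible with uniformly good and uniformly poor ratings. Neither supports nor refutes the hypothesis. With no estimate or threshold fixed in advance, subgroup p-values could be reported as evidence of impact, or a cut-off for positive experience could be chosen after the scores are seen.

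**Working it through.** The defect does not rest on a figure, so the first three steps set the parts of the SAP side by side. The fourth gives the precision that the proposed estimate would have.

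**1. Who supplies scores.** The PASC-EQ concerns using the checklist in the intervention arm. The PASC-IQ items belong to the same survey and concern the implementation of PASC. A control-period patient has neither to rate. The section mentions no control-period administration, no before–after measurement and no external norm. That there are no control scores is therefore an inference, though a strong one.

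**2. What each named test can show.**

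| Planned analysis | Contrast | Bears on impact? | Bears on whether experience is positive? |
|---|---|---|---|
| Chi-squared | Intervention clusters, patient characteristics | No | No |
| t-test / ANOVA | Undefined groups, patient characteristics | Only if groups means trial arms | No |
| Linear model | Adjusts between the same groups, compares across domains | Same condition | No |

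Example: if every ward averaged 1.0, or every ward averaged 3.5, an ANOVA across wards would find no difference either time. Yet the first is a poor experience and the second a good one.

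**3. Comparison with the other surveys.** The SAP sections on the PASC-HEI, the EQ-5D-3L and the HLQ each name a comparison between the trial arms. The PASC-EQ/PASC-IQ section names intervention clusters instead. Its only sample-size argument, more than 200 respondents, concerns confirmatory factor analysis; it gives no effect size, SD or comparator. Power for an impact test therefore cannot be computed from it.

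**4. Precision of a cluster-aware domain mean.**

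Inputs from the SAP: 200 respondents (its stated minimum for factor analysis) and 7 clusters. Assumptions: equal ward sizes, SD 0.7 to 1.2, ICC 0.01 to 0.10. The SAP gives no SD for these scores. Its ICC of 0.05 belongs to the complications calculation and is used here only as a middle value.

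- Respondents per ward: m = 200 / 7 = 28.6
- Design effect: DE = 1 + (m − 1) × ICC
- Standard error: SE = SD / √200 × √DE
- Half-width: 2.447 × SE, where 2.447 is the 97.5% point of t with 7 − 1 = 6 df

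| SD | ICC | DE | SE | 95% half-width |
|---|---|---|---|---|
| 0.7 | 0.01 | 1.28 | 0.056 | 0.14 |
| 1.0 | 0.05 | 2.38 | 0.109 | 0.27 |
| 1.2 | 0.10 | 3.76 | 0.164 | 0.40 |

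The df of 6 is a choice made for this interval. It is not a figure in the SAP.

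**The case against.** The strongest reply is that the section does not say to whom the questionnaires were sent. It says what the PASC-EQ was developed to measure. The domain labels, such as communication with healthcare personnel, are not specific to the checklist, and the items are not shown. The groups in the t-test sentence could be the trial arms. This stands in part: a reader might state as fact that there were no control respondents, and that the ANOVA is purely between wards, but the SAP says neither. The reply does not rescue the plan, though. If arms were meant, the section would conflict with its own description of the instrument and would still need correcting.

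A second reply is that the summary under c) already words the implementation hypothesis descriptively. That is correct, so a reader should not infer that both questionnaires carry an untestable causal hypothesis throughout the SAP. For the PASC-IQ the defect is narrower: inconsistent wording, and no reference value or one-sample estimate. The phrase restricting measurement to the intervention arm also describes the PASC-EQ alone; for the PASC-IQ the restriction follows from its being part of the same survey.

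Third, much of the section concerns validity and reliability, which need no control arm. That is fair, and those analyses are untouched.

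Fourth, the precision figures depend on an assumed SD and ICC, and they describe the remedy, not the harm. This is accepted, which is why a range is given. A single half-width such as 0.27 should not be taken to mean that a mean of 2.3 would reliably be separated from 2. At SD 1.0 and ICC 0.05, power for a true mean of 2.3 is about 0.63, and over the assumed range it runs from 0.34 to 0.99.

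**Conclusion.** The point holds. The hypothesis stated for the PASC-EQ and PASC-IQ and the tests assigned to it do not fit together. As written, the tests can show differences between wards or subgroups, but not that PASC improved experience or that experience is positive. This is more than missing detail that a protocol might supply, because the SAP itself states the hypothesis, the measured population and the tests.

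The conclusion rests on two readings: that the survey covers intervention patients only (inferred from the instrument description), and that *groups* does not mean trial arms (supported by the reference to intervention clusters just before it, but not stated). It is confined to these two questionnaires and does not touch the analysis of complications.

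It does not follow that the data are uninformative. A descriptive question can be answered with one arm, with a half-width of about 0.14 to 0.40 points under the stated assumptions. The plan should be changed before these scores are analysed.

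**What to change.** - Align the hypotheses in the opening summary and in the PASC-EQ/PASC-IQ section to the descriptive wording already used under c), and do not conclude an impact of PASC from these questionnaires.
- Make the primary analysis the mean score of each domain with a 95% confidence interval that allows for ward clustering, plus the share of answers in the top two agreement categories.
- Judge the means against a reference value fixed before analysis. The neutral score of 2 is one candidate, once all items are confirmed to be positively worded or reverse-scored.
- Label comparisons between wards and between patient subgroups exploratory.
- If *groups* was meant as trial arms, say so and reconcile this with the description of the instrument.

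The change needs revised wording and one simple estimate per domain, with no new data. It does restate a primary hypothesis in a plan last updated on 30 August 2024, so it should be dated and justified as made before analysis. The price is a weaker, descriptive claim spread over up to eight domains (five PASC-EQ, three PASC-IQ), so the plan should also say how those eight results will be read together.
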